9.1.3 Intensity

The intensity assessment for a clinical AE must be completed using the following definitions as guidelines:

Assessment of Intensity	
MILD	A type of AE that is usually transient and may require only minimal treatment or therapeutic intervention. The event does not generally interfere with usual activities of daily living.
MODERATE	A type of AE that is usually alleviated with additional specific therapeutic intervention. The event interferes with usual activities of daily living, causing discomfort but poses no significant or permanent risk of harm to the research participant.
SEVERE	A type of AE that interrupts usual activities of daily living, or significantly affects clinical status, or may require intensive therapeutic intervention.

An event is defined as *serious* when it meets at least one of the predefined outcomes as described in the definition of an SAE, NOT when it is rated as severe.

9.1.4 Assessment of Causality

Assessment of Causality

• The investigator is obligated to assess the relationship between study intervention and each occurrence of each AE or SAE.• A reasonable possibility of a relationship conveys that there are facts, evidence, and/or arguments to suggest a causal relationship, rather than a relationship cannot be ruled out.• The investigator will use clinical judgment to determine the relationship.• Alternative causes, such as underlying disease(s), concomitant therapy, and other risk factors, as well as the temporal relationship of the event to study intervention administration will be considered and investigated.• The investigator will also consult the investigator's brochure in his/her assessment.• For each AE or SAE, the investigator must document in the medical notes that he/she has reviewed the AE or SAE and has provided an assessment of causality. In evaluating causality, the investigator will need to make a Yes/No assessment (ie, related or not related) regarding a reasonable possibility that the study intervention caused the event.• There may be situations in which an SAE has occurred and the investigator has minimal information to include in the initial report to the sponsor. However, it is very important that the investigator always make an assessment of causality for every event before the initial transmission of the SAE data to the sponsor.• The investigator may change his/her opinion of causality in light of follow-up information and send an SAE follow-up report with the updated causality assessment.• The causality assessment is one of the criteria used when determining regulatory reporting requirements.

9.1.5 Follow-up of Adverse Events and Serious Adverse Events

After the initial AE/SAE report, the investigator is required to proactively follow each participant at subsequent visits/contacts. All AEs/SAEs and non-serious AEs of special interest (as defined in Section 6.5.2) will be followed until resolution, stabilization, the event is otherwise explained, or the participant is lost to follow-up (as defined in Section 8.8).

The investigator is obligated to perform or arrange for the conduct of supplemental measurements and/or evaluations as medically indicated or as requested by the sponsor to elucidate the nature and/or causality of the AE or SAE as fully as possible. This may include

additional laboratory tests or investigations, histopathological examinations, or consultation with other health care professionals.

New or updated information will be recorded in the originally completed eCRF.

The investigator will submit any updated SAE data to the sponsor within 24 hours of receipt of the information.

9.1.6 Adverse Reactions, Serious Adverse Reactions, and Suspected Unexpected Serious Adverse Reactions

For the purposes of expedited reporting within the EU, the sponsor will follow the applicable definitions for ARs, SARs, and SUSARs (for example, as outlined in Article 2 [n,o,p] of Directive 2001/20/EC, see below). Also, seriousness criteria for AEs/ARs (as would apply to SARs and SUSARs) are currently included in the protocol, listed in Section 9.1.2.

- Adverse Reaction: all untoward and unintended responses to an investigational medicinal product related to any dose administered
- Serious Adverse Reaction: an adverse reaction that results in death, is life-threatening, requires hospitalisation or prolongation of existing hospitalisation, results in persistent or significant disability or incapacity, or is a congenital anomaly or birth defect (see Section 9.1.2 for further details pertaining to seriousness criteria)
- Suspected Unexpected Serious Adverse Reaction: a serious adverse reaction, the nature or severity of which is not consistent with the applicable product information (eg, the Investigator's Brochure).

9.2 Procedures for Reporting Adverse Events

Any AE must be recorded on the appropriate CRF.

All AEs that are drug-related and unexpected (not listed as treatment-related in the current investigator's brochure) must be reported to the governing IRB/IEC as required by the IRB/IEC, local regulations, and the governing health authorities. Any AE that is marked 'ongoing' at the exit visit must be followed-up as appropriate.

9.3 Procedures for Reporting a Serious Adverse Event

Any SAE occurring during the study period (beginning with informed consent) until the Follow-up Visit (Visit 8) or 30 days after the last dose of study intervention if the Follow-up Visit is not done must be immediately reported but no later than 24 hours after learning of an SAE.

SAEs must be reported to the sponsor (or agent of the sponsor) as listed on the Study Contacts Page and recorded on the SAE form. All participants with an SAE must be followed up and the outcomes reported. The investigator must supply the sponsor and the IRB/IEC with any additional requested information (eg, autopsy reports and discharge summaries).

9.3.1 Regulatory Reporting Requirements for Serious Adverse Events

- Prompt notification by the investigator to the sponsor of an SAE is essential so that legal obligations and ethical responsibilities towards the safety of participants and the safety of a study intervention under clinical investigation are met.
- The sponsor has a legal responsibility to notify both the local regulatory authority and other regulatory agencies about the safety of a study intervention under clinical investigation. The sponsor will comply with country-specific regulatory requirements relating to safety reporting to the regulatory authority, IRBs/IECs, and investigators
- Investigator safety reports must be prepared for SUSARs according to local regulatory requirements and the sponsor's policy and forwarded to investigators as necessary.
- An investigator who receives an investigator safety report describing an SAE or other specific safety information (eg, summary or listing of SAEs from the sponsor will review and then file it along with the investigator's brochure and will notify the IRB/IEC, if appropriate according to local requirements.

9.4 Exposure to Study Intervention During Pregnancy

Details of all pregnancies in female participants and female partners of male participants will be collected after the start of study intervention and until the Follow-up Visit (Visit 8) or 30 days after the last dose of study intervention if the Follow-up Visit is not done. Study center personnel must report every pregnancy on the Pregnancy Form (within 24 hours of learning of the pregnancy to the Serious Adverse Event Reporting [contact] [back up [contact]], email: [contact]), even if no AE has occurred. The pregnancy must be followed to term and the outcome reported by completing a follow-up Pregnancy Form. Abnormal pregnancy outcomes (eg, spontaneous abortion, fetal death, stillbirth, congenital anomalies, ectopic pregnancy) are considered SAEs. Elective abortions can be SAEs or AEs depending on the reason for the elective abortion (eg, fetal death, still birth, congenital anomalies, ectopic pregnancy, which would make the elective abortion an SAE). For pregnancy related SAEs, in addition to the Pregnancy Form, a separate SAE Form must be filed as described in Section 9.3 with the appropriate serious criterion (eg, hospitalization) indicated.

9.5 ALT or AST Elevations

A treatment-emergent ALT $\geq 3 \times$ ULN and/or AST $\geq 3 \times$ ULN is considered an AE of special interest. Any participant with this laboratory result after study intervention was taken must have repeat testing within 48 to 72 hours to confirm the abnormality. For this repeat testing, the following laboratory tests must be drawn: hematology and chemistry panels, INR, serum acetaminophen level, urine drugs of abuse screen, and blood alcohol level. An extra blood serology sample must be collected and sent to the central laboratory for further diagnostic testing, at a later date, if needed. In addition, the investigator will perform a complete history and examination to evaluate the participant for possible liver disease.

All AEs of special interest must be reported to the sponsor within 24 hours of the time the investigator becomes aware of the event using the abnormal liver function reporting form and the AE eCRF. All new elements of history, physical examination, diagnostic testing results, and other relevant medical reports are to be reported for each AE of special interest.

If an ALT or AST $\geq 3 \times$ ULN is confirmed, close medical follow-up is required:

For these participants, the following laboratory tests must be performed: anti-hepatitis A IgM, hepatitis B surface antigen, anti-hepatitis B core IgM, hepatitis C antibody, hepatitis C quantitative RNA by polymerase chain reaction, anti-hepatitis E IgM, anti-hepatitis E IgG, Cytomegalovirus IgM antibody, and Epstein-Barr Virus IgM antibody. The participant must be followed clinically and further medical evaluation (for other causes of acute hepatic injury) should be done per the judgment of the investigator and in conjunction with medical personnel at the sponsor. In general, the chemistry panel should be repeated 1 to 2 times per week to follow the course of ALT/AST elevation.

Study intervention must be discontinued if any of the following criteria are met:

- ALT or AST $\geq 3 \times$ ULN and the participant is symptomatic with the appearance of fatigue, nausea, vomiting, right upper quadrant pain or tenderness, fever, rash, or eosinophilia ($> 5\%$)
- ALT or AST $\geq 3 \times$ ULN and total bilirubin $> 2 \times$ ULN
- ALT or AST $\geq 3 \times$ ULN and INR > 1.5
- ALT or AST $\geq 5 \times$ ULN for more than 2 weeks
- ALT or AST $\geq 8 \times$ ULN

The participant may be rechallenged with study intervention only after consultation with the sponsor medical monitor. For participants who are not rechallenged with study intervention, the

participant should be discontinued from the study and complete an ET visit (Visit 7/ET) and 4-week follow-up visit. Participants should receive appropriate follow-up as per standard of care.

The investigator must contact the sponsor medical monitor to discuss all cases of confirmed ALT/AST elevation $\geq 3 \times \text{ULN}$. All ALT/AST elevations must be followed until ALT and AST return to $< 1.5 \times \text{ULN}$ and there is full clinical resolution.

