11.2 CLINICAL LABORATORY PARAMETERS

Descriptive statistics for clinical laboratory values (in International System of units [SI]) at baseline, postbaseline, and changes from baseline values at each postbaseline timepoint will be presented by treatment group for the following laboratory parameters:

Hematology: Hemoglobin, hematocrit, red blood cell count, red blood cell indices (mean corpuscular volume, mean corpuscular hemoglobin, mean corpuscular hemoglobin concentration), white blood cell count, white blood cell count differential (neutrophils, lymphocytes, monocytes, eosinophils, and basophils), and platelet count

Chemistry: Sodium, potassium, chloride, bicarbonate, glucose, blood urea nitrogen, creatinine, total bilirubin, alkaline phosphatase, aspartate aminotransferase, alanine aminotransferase, lactate dehydrogenase, creatine kinase, total protein, albumin, calcium, phosphorus, uric acid, total cholesterol, estimated glomerular filtration rate

Urinalysis: Specific gravity, pH

In addition, descriptive statistics for values and changes from the baseline values in conventional units at each assessment time point will be presented for selected clinical laboratory parameters listed in Appendix 20.1. A description of reporting the lab values in conventional units in participant narratives (along with the standard reporting in SI units) is presented at the end of Appendix 0.

Clinical laboratory test values will be considered potentially clinically significant (PCS) if they meet either the lower-limit or higher-limit PCS criteria listed in Table 11.2-1. The number and percentage of participants who have PCS postbaseline clinical laboratory values will be tabulated by treatment group. The percentages will be calculated relative to the number of participants with available non-PCS baseline values and at least 1 postbaseline assessment for the double-blind

treatment period. The numerator will be the total number of participants with available non-PCS baseline values and at least 1 PCS postbaseline value during the study. A supportive tabular display of participants with PCS postbaseline values will be provided, including the participant identification (PID) number, baseline and all postbaseline (including non-PCS) values.

In addition, a tabular display showing all AEs that occurred in participants who had PCS postbaseline clinical laboratory values will be provided.

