Shift tables from baseline to end of double-blind treatment period for clinical laboratory parameters will be presented by treatment group for the following categories: low, normal, and high, which are provided by lab vendor.

Participants who meet the potential Hy's Law criteria from the first dose of study drug to the end of study will be summarized. Supportive tabular displays will also be provided.

Table 11.2-1. Criteria for Potentially Clinically Significant Laboratory Results

Parameter	SI Unit	Lower Limit	Higher Limit
CHEMISTRY			
Albumin	g/L	< 0.8 × LLN	> 1.2 × ULN
Alanine aminotransferase	U/L	—	≥ 3.0 × ULN
Alkaline phosphatase	U/L	—	≥ 3.0 × ULN
Aspartate aminotransferase	U/L	—	≥ 3.0 × ULN
Bicarbonate	mmol/L	< 0.9 × LLN	> 1.1 × ULN
Bilirubin, total	μmol/L	—	≥ 1.5 × ULN
Blood urea nitrogen	mmol/L	—	> 1.5 × ULN
Calcium	mmol/L	< 0.9 × LLN	> 1.1 × ULN
Chloride	mmol/L	< 0.9 × LLN	> 1.1 × ULN
Cholesterol, total	mmol/L	—	> 1.6 × ULN
Creatinine	μmol/L	—	> 1.5 × ULN
Creatine kinase	U/L	—	> 2.0 × ULN
Estimated glomerular filtration rate	mL/min/1.73m ²	<60 mL/min/1.73m ²	—
Glucose, nonfasting	mmol/L	< 0.8 × LLN	> 2.0 × ULN
Lactate dehydrogenase (LDH)	U/L	—	> 3.0 × ULN
Phosphorus	mmol/L	< 0.9 × LLN	> 1.1 × ULN
Potassium	mmol/L	< 0.9 × LLN	> 1.1 × ULN
Protein, total	g/L	< 0.9 × LLN	> 1.1 × ULN
Sodium	mmol/L	< 0.9 × LLN	> 1.1 × ULN
Uric acid	μmol/L	—	> 1.2 × ULN
HEMATOLOGY			
Basophils, absolute cell count	10 ⁹ /L	—	> 2.0 × ULN
Eosinophils, absolute cell count	10 ⁹ /L	—	> 2.0 × ULN
Hematocrit	Ratio	< 0.9 × LLN	> 1.1 × ULN
Hemoglobin	g/L	< 0.9 × LLN	> 1.1 × ULN
Lymphocytes, absolute cell count	10 ⁹ /L	< 0.7 × LLN	> 1.3 × ULN
Monocytes, absolute cell count	10 ⁹ /L	< 0.5 × LLN	> 2.0 × ULN
Neutrophils, absolute cell count	10 ⁹ /L	< 0.7 × LLN	> 1.3 × ULN
Platelet count	10 ⁹ /L	< 0.5 × LLN	> 1.5 × ULN
Red blood cell count	10 ¹² /L	< 0.9 × LLN	> 1.1 × ULN
White blood cell count	10 ⁹ /L	< 0.9 × LLN	> 1.5 × ULN
URINALYSIS			
pH	pH	< 0.9 × LLN	> 1.1 × ULN
Glucose	—	—	At least 1+
Protein	—	—	At least 1+
Specific gravity	—	—	> 1.1 × ULN

LLN = lower limit of normal value; ULN = upper limit of normal value; normal value provided by laboratory.

SI = Le Système International d'Unités (International System of Units).

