	Week 12	Visit 7/ET	Treatment Day [70, end of the double-blind treatment period]

ET = early termination.

Table 16.1-14. Efficacy Analysis Visit Definitions in the Off-Treatment Hypothetical Estimand Approach for Patient Satisfaction with Study

Analysis Phase	Analysis Visit (Derived)	Window
On or after the first dose of study intervention	Week 4	Treatment Day [2, 41]
	Week 8	Treatment Day [42, 69]
	Week 12	Treatment Day [70, end of last study visit]

The analysis visit windows for MIDAS and PHQ for mITT Population and Off-treatment Hypothetical Estimand Population are defined as follows:

Table 16.1-15. Efficacy Analysis Visit Definitions for MIDAS and PHQ

Analysis Phase	Analysis Visit (Derived)	Scheduled Study Visit (eCRF)	Window
Pretreatment	Baseline	Visit 2 (Randomization)	Treatment Day \leq 1
Double-blind Treatment Period	Week 12	Visit 7/ET	Treatment Day [2, end of the double-blind treatment period]

Table 16.1-16. Efficacy Analysis Visit Definitions in the Off-Treatment Hypothetical Estimand Approach for MIDAS and PHQ

Analysis Phase	Analysis Visit (Derived)	Window
Pretreatment	Baseline	Treatment Day \leq 1
On or after the first dose of study intervention	Week 12	Treatment Day [2, end of last study visit]

The analysis visit windows for safety endpoints are defined as follows:

Table 16.1-17. Safety Data Analysis Visit Definitions

Analysis Phase	Analysis Visit (Derived)	Scheduled Study Visit (eCRF)	Window
Pretreatment	Baseline	Visit 2 (Randomization)	Treatment Day ≤ 1
Double-Blind Treatment Period	Week 2	Visit 3	Treatment Day [2, 20]
	Week 4	Visit 4	Treatment Day [21, 34]
	Week 6	Visit 5	Treatment Day [35, 48]
	Week 8	Visit 6	Treatment Day [49, 69]
	Week 12	Visit 7/ET	Treatment Day [70, end of the Double-blind Treatment Period]
	End of Double-blind Treatment Period		Last available assessment during double-blind treatment period
	Week 16 (Safety follow-up)	Visit 8	Treatment Day [end of double-blind treatment period +1, end of safety follow-up period]
	Estimand Follow-up		Treatment Day [end of safety follow-up period +1, the last study visit]
	End of study		Last available assessment after treatment start date, i.e. occurs at final visit (expected Day 112) or ET

Safety follow-up visit will be presented in analysis tables for clinical laboratory values and vital signs.

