End of Double-blind Treatment Period is defined as the last available assessment during double-blind treatment period. End of Double-blind Treatment Period results will be presented in analysis tables for clinical laboratory values and vital signs.

End of Study is defined as the last available assessment during the study, including double-blind and safety follow-up period.

End of Study results will be presented in analysis tables for safety parameters, including but not limited to electrocardiograms, clinical laboratory values, and vital signs.

ET = early termination.

For endpoints collected by visit (not for eDiary data), if a participant has 2 or more visits within the same window, the last visit with a non-missing value will be used for analysis, unless specified otherwise.

The following algorithm is used to define the double-blind treatment period and the follow-up periods unless specified otherwise. The double-blind treatment period starts with the date of the first dose of double-blind study treatment and ends with the latest date of the last study medication date, and the last scheduled assessment date of Visit 2 to Visit 7 for participants who entered the safety follow-up period; or ends with the latest date of the last study medication date, and last assessment date for participants who did not enter the safety follow-up period. The safety follow-up period starts with the 1 day after the end of the double-blind period and ends with the last scheduled assessment date of Visit 8 for participants who entered the estimand follow-up period;

or ends with the last assessment date for participants who did not enter the estimand follow-up period. The estimand follow-up period starts with the 1 day after the end of the safety follow-up period and ends with the last assessment date for participants who entered the estimand follow-up period.

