16.3 REPEATED OR UNSCHEDULED ASSESSMENTS OF SAFETY PARAMETERS

If a participant has repeated assessments before the start of the first treatment, the results from the final nonmissing assessment made prior to the start of the study treatment will be used as baseline. If a participant has 2 or more visits within the same window, the last visit with a nonmissing value will be used for summary over time. If end-of-study assessments are repeated or if unscheduled visits occur, the last nonmissing postbaseline assessment will be used as the end-of-study assessment for generating summary statistics. However, all postbaseline assessments will be used for PCS value determinations, and all assessments will be presented in the data listings.

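### Repeat liver tests triggered by an ALT/AST rise replace the triggering value in the by-visit laboratory summaries at Visits 3 to 6 (minor; case detection is unaffected)

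*Protocol*

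**What the plan says.** **When extra samples are drawn.** Under Protocol 9.5, a participant with treatment-emergent ALT or AST at or above 3 × ULN "must have repeat testing within 48 to 72 hours to confirm the abnormality". Once the rise is confirmed, "In general, the chemistry panel should be repeated 1 to 2 times per week to follow the course of ALT/AST elevation". Follow-up then has an end point: "All ALT/AST elevations must be followed until ALT and AST return to" below 1.5 × ULN, with clinical resolution.

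**Which value the tables use.** SAP 11.2 plans laboratory descriptive statistics in which "changes from baseline values at each postbaseline timepoint will be presented by treatment group". SAP 11.0 lists the statistics, which include the mean and maximum. When a window holds two or more visits, SAP 16.3 (the section on repeated or unscheduled safety assessments) says "the last visit with a nonmissing value will be used for summary over time". SAP 16.1 has the same rule for data collected by visit.

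**Shift table.** SAP 11.2: "Shift tables from baseline to end of double-blind treatment period for clinical laboratory parameters will be presented by treatment group". SAP 16.1: "End of Double-blind Treatment Period is defined as the last available assessment during double-blind treatment period".

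**What uses every value.** SAP 16.3 keeps all postbaseline assessments for PCS determinations and lists them. Table 11.2-2 counts a participant with any postbaseline value in a hepatic category. Potential Hy's law cases and adjudicated cases at or above 3 × ULN are summarized separately.

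**The concern.** The repeats required by Protocol 9.5 are triggered by the outcome itself. A rule that prefers the last value in a window therefore lets the outcome decide which sample enters the by-visit summary. A participant without a rise normally contributes the scheduled draw. A participant with a rise contributes a later draw, taken while the rise is being followed and possibly after study drug has stopped.

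ALT/AST elevation is an event of special interest in this protocol, and Protocol 1.2 reports that serum ALT increases ended development of an earlier oral CGRP antagonist. At stake is consistency of presentation. A by-visit ALT table could omit the very value that puts the participant in the hepatic-category table beside it.

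**Working it through.** The plan states no figure for this effect, so there is none to reproduce. The check is whether a repeat and its triggering draw share a window, and then what the period-end rules do at Visit 7.

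**Inputs.** Visit days and the ±3-day allowance for Visits 3 to 6 come from Protocol Table 1. Safety windows and period-end rules come from SAP 16.1 (windows in Table 16.1-17). The 2 or 3 days to the repeat come from Protocol 9.5.

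| Visit | Nominal day | Safety window | Days left after nominal day |
|---|---|---|---|
| 3 | 14 | 2 to 20 | 20 − 14 = 6 |
| 4 | 28 | 21 to 34 | 34 − 28 = 6 |
| 5 | 42 | 35 to 48 | 48 − 42 = 6 |
| 6 | 56 | 49 to 69 | 69 − 56 = 13 |

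**By-visit tables, Visits 3 to 6.** Each visit has 7 possible days (nominal ±3) and 2 possible delays, giving 14 combinations.

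- If the 48 to 72 hours run from the draw, the repeat is in the same window in 14 of 14 combinations at every visit. The latest case at Visit 3 is 17 + 3 = Day 20, still inside.
- If they run from receipt of the result, assumed to be 1, 2 or 3 days after the draw, 13, 11 or 9 of 14 remain inside at each of Visits 3, 4 and 5. At Visit 6 it is 14 of 14 throughout.
- A repeat that crosses into the next window is normally superseded there by the next scheduled draw.
- Further panels once or twice a week fit most easily in the Week 8 window.

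So at Visits 3 to 6 the by-visit statistics normally carry a repeat in place of the triggering value.

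**Visit 7.** A draw on Day 84 to 87 has its repeat on Day 86 to 90.

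- For a participant who enters safety follow-up, the double-blind period ends at the later of the last dose and the last scheduled assessment from Visits 2 to 7. The repeat falls outside, assuming dosing does not continue past Visit 7, and replaces nothing.
- For a participant who does not enter follow-up, the period runs to the later of the last dose and the last assessment. A repeat recorded in this study then replaces both the Week 12 and the end-of-period value. Rollover participants are the obvious example, because Protocol 3.1 does not require Visit 8 for them.

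**Shift table.** Its postbaseline value is usually the scheduled Visit 7/ET draw. A rise at Visits 3 to 6 that has resolved by then is absent with or without repeats. The cause is that the table uses the last value and not the worst one.

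**Illustrative size.** Change in arm mean at one visit = m × (first − last) / 250, with m participants affected and values in multiples of ULN. The 250 is the planned arm size; m and the two values are assumptions.

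- Low end: 1 × (3 − 1.5) / 250 = 0.006 × ULN.
- High end: 5 × (8 − 1) / 250 = 0.14 × ULN.

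Both are falls. A repeat higher than the triggering value moves the mean the other way.

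**The case against.** The strongest reply is that these are untested descriptive tables and that every output meant to find liver injury uses all values. That is correct, and it limits the point to presentation. A reader might infer that the liver signal is hidden; SAP 11.2 and 16.3 do not support that.

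Four other tempting readings also fail.

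- **That the bias always runs towards no effect.** The rule takes the last value, not the lowest. The 48 to 72 hour repeat exists to confirm the abnormality and may be similar or higher. The later panels are worded as general guidance, not as a strict requirement.
- **That repeats overwrite the shift table.** They do so only after Visit 7 and only for participants who do not enter follow-up. A last repeat at 1.5 × ULN would still be above the normal range and so still classed as high.
- **That extra samples exist only for participants with a rise.** Protocol 6.5.3 allows unscheduled laboratory tests for any participant's safety. What differs is that a rise makes a repeat mandatory.
- **That the shift is large against the standard error of the mean change.** The documents give no ALT standard deviation, and the elevated values assumed in such a comparison would themselves inflate it.

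The reply also notes that a worst-value shift is largely in the plan already. Table 11.2-2 starts at 1 × ULN for any postbaseline value, and exclusion criterion 13 bars ALT or AST above 1 × ULN at Visit 1 (likewise bilirubin, except in Gilbert's disease). That row is therefore close to a normal-to-high shift at the maximum, which is why the added shift table is only optional.

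What the reply does not remove is the outcome-dependent choice of value in the by-visit ALT/AST statistics.

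**Conclusion.** The point holds for the by-visit ALT/AST summaries at Visits 3 to 6. There a triggered repeat normally replaces the triggering scheduled value and can move the mean and maximum in either direction, depending on whether values are falling or rising. For the shift table the main limitation is that it uses the last double-blind value; displacement by repeats is confined to participants who do not enter safety follow-up.

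The size cannot be derived from the documents, which give no expected elevation rate or time course. The 0.006 to 0.14 × ULN range is an illustration that assumes all affected participants rise at the same visit. Severity is minor: case detection, sample size, type I error and efficacy are untouched.

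**What to change.** In SAP 16.1 and 16.3, state that by-visit laboratory summaries use the scheduled-visit sample and take an unscheduled sample only when the scheduled one is missing. Say also which draw counts when an early-termination draw shares a window with a scheduled visit, for example the one closest to the nominal day. Keep every value for the PCS, hepatic-category, potential Hy's law and adjudication outputs, as now.

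Optionally, add a shift table from baseline to the maximum postbaseline value for ALT, AST and bilirubin, noting that Table 11.2-2 already covers most of it.

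The cost is a short SAP edit, a little more programming and, if wanted, one extra table. The repeat-testing schedule in Protocol 9.5 is not affected.
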